### Exclusion criteria:

1. Currently involved in another intervention study.
2. Transferred to the intensive care unit or isolation-room stay.
3. Currently on a ventilator or extracorporeal membrane oxygenation

(ECMO) machine.

4. Currently have a ventricular assist device (VAD) or an automatic implantable cardioverter-defibrillator (AICD).
5. Advanced heart failure - ejection fraction of < 20%.
6. Documented cardiovascular risk from exercise.
7. Resting heart rate <50 bpm or >120 bpm.
8. Uncontrolled or new (within 24 hours) arrhythmias.
9. Resting blood pressure below 90/70 or above 160/100.
10. Oxygen saturation (O2 sat) < 90% during rest.
11. Uncontrolled or severe orthostatic hypotension that limits standing tolerance.
12. Cardiac ischemia within 24 hours.
13. Unresolved or new (within 24 hours) deep vein thrombosis.
14. Concurrent severe neurological pathology/disease or stroke within 72 hours.
15. Open skin ulcerations on any body surfaces in contact with exoskeleton.
16. Acute fracture
17. Osteoporosis
18. Active heterotrophic ossification (HO) of the lower extremity, hip dysplasia, or hip/knee axis abnormalities.
19. Current chemotherapy
20. Inability to speak or understand the English language.
21. Inability to cooperate in tests/exercises.
22. Hip flexion contracture greater than ~17°.
23. Knee flexion contracture greater than 12°.
24. Unable to achieve neutral ankle dorsiflexion with passive stretch (neutral with max 12° knee flexion).
25. Cognitive impairments - unable to follow 2 step commands or to communicate pain or to stop session.
26. Pregnancy
27. Any reason the physician may deem as harmful to the participant to enroll or continue in the study.

- Sample Size:** Forty (40) Participants who meet the inclusion and exclusion criteria will be enrolled.
- Blinding:** Blinding will not be implemented during this study.
- Setting/Sites:** Hospital, long-term care facilities, or skilled nursing facilities (up to 5 clinical sites). Sites are to be chosen based on having Ekso Level 2 training certification, location, enrollment capabilities, and resources.
- Duration:** Each enrolled Participant is expected to engage in this study for up to 2 weeks. The duration of the study is expected to be approximately 6 months.
- Assessment periods:** The study consists of a screening period and up to 5 training sessions with assessments for safety.

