## **4. Study Endpoints**

The primary endpoint is safety defined as the number of device-related serious adverse events per Participant and overall during the study period.

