## **12. Adverse Events**

An adverse event (AE) is any untoward medical event that occurs to a study Participant once the individual has signed the informed consent form until the study Participant's last study visit.

Examples include:

- Any sign, symptom, or physical examination finding that worsens in nature, severity or frequency compared to baseline.

A serious adverse event (SAE) is one that meets any of the following criteria:

- Results in death.
- Is life threatening.
- Requires inpatient hospitalization or prolongation of an existing hospitalization.
- Results in persistent or significant disability/incapacity.
- An important medical event that may not result in death, be life-threatening, or require hospitalization, may be considered a serious adverse event when, based upon appropriate medical judgment, it jeopardizes the Participant and may require medical or surgical intervention to prevent one of the outcomes listed in this definition.

A life-threatening adverse event is defined as any adverse experience that places the Participant, in the view of the Investigator, at immediate risk of death from the event as it occurred, i.e. it does not include an event that, had it occurred in a more severe form, might have caused death. ALL serious adverse events must be reported to the Sponsor within 24 hours of the knowledge of the event and reported to the respective IRB as soon as possible, but no later than ten working days after the investigator learns of the event or as required by the IRB. In the event of Participant death, a copy of

death records, medical records pertaining to the events leading up to the death and an autopsy report (if performed) must be sent to the Sponsor as soon as possible. All Participant identifiers other than the Participant number and initials must be removed from the documents submitted to the Sponsor.

A pre-existing condition is one that is present prior to or at the start of the study and is to be reported as part of the Participant's medical history. It should be reported as an adverse event only if the frequency, intensity, or the character of the condition worsens during study participation.

An unanticipated adverse event is one not identified in nature, severity, or frequency in the current protocol.

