Adverse events (AE) data collection must begin once the Participant has signed the informed consent document. AEs will continue to be collected each visit during the entire 12-week training period and end at the 6-month visit. In general, AEs should be reported and classified by the investigator using a diagnosis. The diagnosis should be confirmed through specific signs, symptoms, and (if necessary) laboratory tests. Data to be collected will include the description of the event, onset and resolution dates (or whether the event is ongoing), severity, management/treatment, outcome, and determination of the relationship to the device used during training. The relationship of the event to the device used will be further described as related or unrelated to a specific device. If related to a device, the categories will be further described as definitely, probably, or possibly-related using the following definitions:

1. *Definitely device-related*: Any event that is associated with the device by timing and physiology, and was caused or contributed to by the device.
2. *Probably device-related*: Any event that is associated with the device by timing and physiology, and there is a good chance that it may have been caused or contributed to by the device.
3. *Possibly device-related*: Any event that is associated with the device by timing and physiology, and there is a possibility that it may have been caused or contributed to by the device.

Severity of the AE will be coded as to the degree of severity as follows:

- A. *Mild*: Awareness of the event, but easily tolerated.
- B. *Moderate*: Discomfort enough to cause interference with usual activity.
- C. *Severe*: Inability to carry out usual activity. (Not necessarily the same as a Serious Adverse Event. Participants may have a severe flu but not require hospitalization.)

Treatment for the AE includes all of the commercially approved products or standard procedures that are to be administered according to standard medical practice. Investigational products or procedures are not to be used as a treatment for an adverse event. All unresolved AEs should be followed by the investigator until all events are resolved, the event is identified as being a chronic condition, or the Participant is lost to follow-up.

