The case report form package for this study includes dedicated adverse event and serious adverse event forms. An independent Data Safety Monitoring Board (DSMB) will assess and adjudicate all SAEs and protocol violations.

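### The DSMB's stated remit gives an event that the site files as non-serious no route to independent review of seriousness, and the protocol does not say whose classification enters the primary count

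*Protocol*

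**What the plan says.** Protocol section 4 defines the outcome: "The primary endpoint is safety defined as the number of device-related serious adverse events per Participant and overall during the study period". An event enters the count only if it is judged serious and judged device-related.

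Section 12 deals with the two judgements separately.

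- **Seriousness.** The criteria include "Requires inpatient hospitalization or prolongation of an existing hospitalization". A further criterion covers an important medical event, which "may be considered a serious adverse event when, based upon appropriate medical judgment, it jeopardizes the Participant".
- **Relatedness.** This is recorded for AEs generally: "The relationship of the event to the device used will be further described as related or unrelated to a specific device". Related events are then graded as definitely, probably or possibly related.
- **First classification.** "In general, AEs should be reported and classified by the investigator using a diagnosis". AEs and SAEs have separate case report forms.
- **Independent review.** "An independent Data Safety Monitoring Board (DSMB) will assess and adjudicate all SAEs and protocol violations".

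The Study Outline adds "Blinding will not be implemented during this study", and the design has one arm. Section 17 plans no statistical methods and reports numbers of adverse events.

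**The concern.** The board is the only independent adjudicator that the protocol names. Its list starts from events already labelled SAEs. If a site files a serious, device-related event on the AE form, nothing in section 12 brings that event to the board for a second look at seriousness. An event filed as an SAE does get that second look.

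This matters more here than in an outpatient trial. Every participant is already admitted to a hospital, long-term care facility, skilled nursing facility or similar. For a hospital inpatient, new admission cannot mark an event as serious, so that criterion reduces to prolonged stay. Short of death, threat to life or lasting disability, the call then rests on prolongation or on medical judgement about importance. A long-term care resident sent to hospital for the same event would meet the admission criterion directly. Classification could therefore differ by type of facility.

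The result is a raw count with no test behind it, so one misfiled form can change the primary finding. If the board and the investigator disagree, the protocol does not say which view is counted.

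**Working it through.** The protocol states no event rate, power or filing accuracy, so there is no figure of its own to reproduce. The check has two parts.

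**1. Tracing events through section 12**

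| Site's filing | Reaches the board as an SAE? | What adjudication could do to the primary count |
|---|---|---|
| Serious, device-related | Yes | Confirm, or remove if re-rated |
| Serious, unrelated | Yes | Add, if re-rated as device-related |
| Non-serious, device-related | No stated route | Nothing |
| Non-serious, unrelated | No stated route | Nothing |

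The second row shows that relatedness is covered in both directions. The third row is the gap. The entries in the last column assume that the board's view governs the count, which the protocol does not say.

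**2. What one missed event is worth (illustration)**

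Inputs: N = 40 (Study Outline). The filing sensitivity s, meaning the probability that a site files a truly serious event as an SAE, is assumed to be 0.7 to 0.9. The calculation also assumes that relatedness is always captured, that events are filed independently, and that monitoring recovers nothing.

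- One true device-related SAE, missed: 1 − s = 1 − 0.9 = 10% to 1 − 0.7 = 30%.
- Two true events, at least one missed: 1 − s² = 1 − 0.81 = 19% to 1 − 0.49 = 51%.

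These figures restate the assumption and carry no information from the trial.

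On the scale of participants with an event, using exact (Clopper–Pearson) two-sided 95% limits:

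- 0/40: upper limit 1 − 0.025^(1/40) = 8.8%.
- 1/40 = 2.5%: upper limit 13.2%.

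For an assumed true rate p per participant, the chance of recording zero is (1 − p·s)^40:

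| p | s = 1 | s = 0.9 | s = 0.8 | s = 0.5 |
|---|---|---|---|---|
| 2.5% | 36.3% | 40.2% | 44.6% | 60.5% |
| 5% | 12.9% | 15.9% | 19.5% | 36.3% |
| 10% | 1.5% | 2.3% | 3.6% | 12.9% |

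At p = 5%, moving from perfect filing to s = 0.8 raises the chance of a zero count by 19.5 − 12.9 = 6.6 percentage points. With moderate misfiling the effect is modest, but it always acts toward a lower count.

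**The case against.** A reader might infer that adjudication can only lower the primary count. The documents do not support that. The board receives all SAEs, including those the site called unrelated, and re-rating one as device-related would raise the count. Nor does the protocol say that the board's decision replaces the investigator's, so even removal of an event is an inference.

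A reader might also infer that the board is the only safeguard. It is not. The Monitor reviews case report forms for accuracy and for signs of risk to participants (section 19). Source records are compared with the forms partly to check AE reporting (section 26). The sponsor looks into AEs attributed to the device, with no restriction to serious ones (section 21). The board also sees protocol violations, which might include an unreported SAE. These checks could bring a misfiled event to light. However, source comparison covers only a sample of records, and none of these checks is described as a review of seriousness.

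Three further points have weight. A misfiled event still appears in the reported AE data. The sentence on classification by the investigator concerns diagnostic labelling more than seriousness, and absence of blinding adds little where there is no comparator. Limiting adjudication to SAEs is a legitimate design choice, and the board's working rules could widen it.

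What remains is that the protocol itself sets the remit, that this remit leaves out the third row of the table above, and that the counting rule is missing.

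**Conclusion.** The point holds in a limited form. Independent review of seriousness runs one way, because an event filed as non-serious has no stated route to the board. Review of relatedness runs both ways for every SAE. Separately, the protocol leaves open whose classification enters the primary endpoint.

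Nothing in the protocol shows that sites will misfile events or that the count will be biased by any particular amount. The 10% to 30% and 19% to 51% figures depend entirely on an assumed filing sensitivity of 70% to 90% and should be quoted only as illustration. What does follow from the design is that, with 40 participants and no planned analysis beyond counts, a single event decides whether the primary result is zero. This is an inexpensive improvement worth making; it does not invalidate the design.

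**What to change.** Amend the DSMB statement at the end of section 12 so that, besides SAEs and protocol violations, the board reviews for both seriousness and device-relatedness every AE that is:

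- rated device-related in any category (definitely, probably or possibly);
- graded severe; or
- followed by withdrawal, or by transfer to intensive care or to an acute hospital.

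State, there or in section 4, that the board's classification is the one counted in the primary endpoint, and show the investigator's count beside it.

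Cost: a wording change in section 12 and in the board's working rules. The board already exists, and with 40 participants and at most 5 sessions each (40 × 5 = 200 sessions) the extra listing should be short. The downside is a few more narratives to prepare, and the count may rise. An event filed as non-serious, unrelated and less than severe, with no withdrawal or transfer, would still not reach the board. Closing that remainder would mean reviewing all AEs.

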### **13. Participant Termination**

Participants will be advised that they may voluntarily withdraw from the study at any time and will

be instructed to notify the investigator immediately if they choose to withdraw. Participants may choose to withdraw for any reason and are not obligated to reveal their reason(s) for withdrawal. Should Participants withdraw prior to study completion, they will be asked to complete the final evaluations. In addition, Participants may be involuntarily withdrawn by the investigator if the investigator believes it is in the best interests of the Participant (e.g., adverse event that prevents further visits).

When the Participant is discharged from the facility, the End of Study CRF must be completed and submitted to the data manager as soon as possible.

#### **14. Data Collection, Management, and Reporting**

Source documents will be used to record demographic and assessment data as well as any adverse events that may occur during the study period. Source document data will be transferred to case report forms that will be submitted to the data manager. Reports will be generated by the data manager periodically. Ekso Bionics reserves the right to use a third-party data manager.

#### **15. Confidentiality of Data**

All information and data sent to the Sponsor, Contract Research Organizations, DSMB, or the Data Manager concerning Participants or their participation in this study will be considered confidential. All data used in the analysis and reporting of this evaluation will be used in a manner without identifiable reference to the Participant. The principal investigator consents to visits by the staff of the Sponsor and its authorized representatives or any other local or national governmental body to review the study Participants' medical records including any test or laboratory data that might have been recorded on diagnostic tests media (e.g., X-rays, video, photographs, etc.).

#### **16. Record Retention**

The study site is required to retain all study records required by the applicable regulations in a secure and safe facility. The study site must consult with the Sponsor before disposal of any study records, and must notify the Sponsor of any change in the location, disposition or custody of the study files. The study site must take measures to prevent accidental or premature destruction of essential documents, that is, documents that individually and collectively permit evaluation of the conduct of a study and the quality of the data produced, including paper copies of study records (e.g., patient charts) as well as any original source documents that are electronic as required by applicable regulatory requirements. All study records must be retained for at least two years after the study is completed. Participant files and other source data must be kept for the maximum period permitted by the hospital, institution or private practice, but not less than two years. These documents should be retained for a longer period, however, if required by the applicable regulatory requirements. The Sponsor must be notified and will assist with retention should the study site be unable to continue maintenance of Participant files for the full two years. It is the responsibility of the study site to inform the Sponsor as to when these documents no longer need to be retained.

#### **17. Statistical Methods**

This is an observational, feasibility study; therefore, statistical methods will not be employed. Data will be reported as a number (n) of adverse events and categories of patient conditions will be assembled.

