## Study Outline

- Study Title:** Exoskeleton Treatment of Deconditioning Due to Limited Ambulation Caused by Illness or Injury
- Sponsor:** Ekso Bionics, Inc.  
[name]  
[name]
- Study Description:** A safety and feasibility study of robotic exoskeleton training in deconditioned patients residing in a healthcare facility.
- Overall goal:** We aim to demonstrate that EksoGT™ robotic exoskeleton training can be performed safely with patients who have been hospitalized and are at risk of experiencing a further decline in their physical condition.
- Rationale:** Patients who are hospitalized for several weeks or months are at a higher risk of decline in physical condition and are also at a higher risk of rehospitalization within 30 days of discharge. A program incorporating robotic exoskeleton training may provide sufficient physical support and challenge for patients to maintain a higher level of physical condition than if they did not undergo exoskeleton training.
- Hypothesis:** Robotic exoskeleton training during hospitalization is safe and feasible.
- Design:** Single-arm safety and feasibility study.
- Participants:** Patients who fulfill the inclusion/exclusion criteria.

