- Primary Objective:** To demonstrate that a multi-day robotic gait training regimen is safe and feasible for deconditioned patients who have been admitted to a healthcare facility.

**Primary End Point:** The primary endpoint is safety defined as the number of device-related serious adverse events per Participant and overall during the study period.

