## **2. Study Objectives**

The primary objective is to demonstrate that a multi-day robotic rehabilitation regimen is safe and feasible in deconditioned patients who have been admitted to a facility.

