## **3. Study Design**

This is a single-arm, short term, safety and feasibility study.

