Treatment will consist of exercise using the EksoGT described below. Dosage (daily or weekly) and progression of settings (challenge) will be highly individualized due to the heterogeneous population to be enrolled in this study. No participant is expected to exceed 5 sessions in the exoskeleton.

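### Section 17 rules out statistical methods by calling an assigned-treatment study observational, so a bare event count would have to carry the claim that the regimen is safe; zero events in 40 leaves risks up to 8.8% unexcluded

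*Protocol*

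**What the plan says.** Protocol Section 17 (Statistical Methods) gives a decision and its reason: "This is an observational, feasibility study; therefore, statistical methods will not be employed". It then describes the output: "Data will be reported as a number (n) of adverse events and categories of patient conditions will be assembled".

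Other sections describe a different kind of study and a more ambitious aim:

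- **Design.** Section 3: "This is a single-arm, short term, safety and feasibility study". It does not use the word observational, and neither does the Study Outline.
- **Treatment.** Section 8: "Treatment will consist of exercise using the EksoGT described below". Section 10 sets a daily session goal of 30 to 45 minutes, or as tolerated, for at most five sessions. Section 9 says that the device is being studied for a new indication.
- **Objective.** The Primary Objective in the Study Outline reads "To demonstrate that a multi-day robotic gait training regimen is safe and feasible for deconditioned patients", and Section 2 repeats it: "The primary objective is to demonstrate that a multi-day robotic rehabilitation regimen is safe and feasible". The overall goal in the Study Outline is, similarly, to show that "robotic exoskeleton training can be performed safely with patients who have been hospitalized".
- **Endpoint.** Section 4 defines the primary endpoint as "the number of device-related serious adverse events per Participant and overall during the study period".

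The Study Outline sets enrolment at 40. The protocol gives no confidence level, no expected rate and no acceptable rate of device-related serious adverse events (SAEs).

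**The concern.** Half of the reason given in Section 17 is wrong. A study that assigns a device as treatment under its own protocol is interventional, so the observational label cannot justify leaving statistical methods out. The other half, feasibility, is correct. It justifies having no hypothesis test, but not leaving the uncertainty of the primary safety result unstated.

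The second difficulty is the gap between aim and output. The endpoint wording already implies a per-Participant figure, so a denominator is within reach. What Section 17 bars, as written, is an interval around that figure. With neither an interval nor an acceptable rate, no result can be tied to the word *demonstrate*. A report of zero device-related SAEs could then be read as showing safety while sizeable risks remain compatible with the data. What is at stake is the safety conclusion, not the collection of data.

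**Working it through.** **Inputs.** Forty enrolled (Study Outline, Sample Size); the endpoint from Section 4. The protocol gives no derivation of 40, so there is no figure of the plan's own to reproduce. A 95% level is assumed. The smaller sample sizes and the true risks below are also assumptions, chosen to show the range.

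**Step 1: no events.** The exact (Clopper-Pearson) upper limit for 0 of n is 1 − 0.025^(1/n) two-sided and 1 − 0.05^(1/n) one-sided. For n = 40:

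- two-sided: 1 − 0.025^(1/40) = 0.0881
- one-sided: 1 − 0.05^(1/40) = 0.0722

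The full 40 is the best case. Enrolment precedes the first session (Sections 5 and 8), and participation can end on withdrawal, discharge or physician removal (Section 6). Sections 20 and 27 also let the sponsor report at interim time-points or on a smaller sample.

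| Treated, 0 events | Two-sided upper limit | One-sided upper limit |
|---|---|---|
| 40 | 8.8% | 7.2% |
| 36 | 9.7% | 8.0% |
| 32 | 10.9% | 8.9% |
| 20 | 16.8% | 13.9% |

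**Step 2: one or two Participants with an event.** Two-sided exact 95% limits for 40 treated:

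- 1/40: 0.06% to 13.2%
- 2/40: 0.6% to 16.9%

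**Step 3: how easily zero events arise.** The chance of no events in 40 is (1 − p)^40 for a true per-Participant risk p:

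- p = 2%: 0.98^40 = 0.446, about 45%
- p = 5%: 0.95^40 = 0.129, about 13%
- p = 10%: 0.90^40 = 0.015, about 1.5%

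**Step 4: does the summary measure matter?** If events are counted rather than Participants with at least one event, the two-sided Poisson upper limit for zero events is −ln(0.025)/40 = 3.689/40 = 0.092 device-related SAEs per Participant. That is close to the binomial 0.088, so the conclusion does not depend on this choice.

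**The case against.** The strongest reply is that feasibility studies are descriptive and that little is lost here. Section 17 does plan counts, Section 4 adds a per-Participant view, and any reader with n and N can compute an exact interval. The observational label looks like a slip, since the design is stated correctly elsewhere. The word *demonstrate* has no test, margin or success rule attached to it, and Section 1 calls the study a pilot in a small group. Statistical methods may have been meant only as hypothesis tests.

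Much of this is fair, and it limits the point. No data are lost and no test is needed. No stated threshold is breached, because there is none. The 8.8% depends on convention: with zero events the lower limit is fixed at 0, so the two-sided limit is in effect a 97.5% one-sided bound, and the 95% one-sided bound is 7.2%. An interval alone would not demonstrate safety either; the objective has to be reworded as well. The proportion of Participants with an event is a companion to the Section 4 count, not the same quantity. Rewording the objective also does not supply a feasibility endpoint, which Section 4 lacks.

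The reply does not rescue the text. Section 17 does not leave the analysis open for a later plan: it rules methods out, so an analysis plan that added an interval would contradict the protocol. If only hypothesis tests were meant, the section does not say so. Adjudication of SAEs by the safety board (Section 12) protects the classification of events, not the precision of the risk estimate.

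**Conclusion.** The concern holds. Section 17 bases a ban on statistical methods partly on a description of the study that the protocol itself contradicts, and the remaining output cannot support the objective of demonstrating safety. In the best case, zero events with all 40 treated, per-Participant risks up to 8.8% (two-sided exact 95%) or 7.2% (one-sided) remain unexcluded; with 20 treated the limits are 16.8% and 13.9%. These figures rest on an assumed 95% level, and the smaller size is illustrative. Since the protocol states no acceptable rate, whether 8.8% would be tolerable cannot be judged. The plan should be changed, although the fault lies in what may be concluded and not in how the study is run.

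**What to change.** 1. In Section 17, describe the study as single-arm interventional feasibility and replace the exclusion of statistical methods with a statement that no hypothesis test is planned.
2. Keep the Section 4 total of device-related SAEs. Add the number and proportion of treated Participants (at least one EksoGT session) with at least one such event, with an exact Clopper-Pearson 95% confidence interval.
3. State in advance that zero events among 40 treated would exclude only risks above 8.8% (two-sided).
4. In the Study Outline (overall goal and Primary Objective) and in Section 2, replace the aim of demonstrating safety with estimating the risk of device-related SAEs and assessing feasibility.
5. As a secondary matter, require any interim or smaller-sample report under Sections 20 or 27 to give the same n/N and exact interval for all Participants treated up to the data cut-off.

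The cost is protocol wording and a few lines of analysis, with no new data, visits or Participants. The price is a safety statement that looks less favourable.
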